### 3.1.2 Sample Size

A maximum of 300 subjects (males and females) will be randomized into the trial. The sample size was based on computer simulations under five sigmoidal dose-response profiles without baseline adjustment. The operating characteristics and associated power were estimated for the different dose-response scenarios by computer simulations using the Fixed and Adaptive Clinical Trial Simulator (FACTS) version 5.6.

The average number of subjects and probabilities for futility and success are presented in Table 2.

**Table 2 Operating Characteristics**

Dose-Response Scenario	Maximum response ( $\alpha_2$ )	ED 50 ( $\alpha_3$ )	Average Number of Subjects	Futility Stopping at First Interim	Total Futility stopping	Power (Total Success)
Null	0	0 $\mu\text{g}$	200	75.8%	97.0%	3.0%
I	-0.3	150 $\mu\text{g}$	277	15.7%	47.9%	52.1%
II	-0.4	200 $\mu\text{g}$	288	7.9%	25.1%	74.9%
III	-0.5	200 $\mu\text{g}$	296	2.8%	9.6%	90.4%
IV	-0.5	350 $\mu\text{g}$	295	3.4%	15.4%	84.6%
V	-0.6	300 $\mu\text{g}$	298	1.4%	2.7%	97.3%

For each dose-response scenario, 1,000 trials were simulated in order to estimate the operating characteristics presented in Table 2. The simulations under the null-hypothesis (no effect) demonstrate that the probability of making a false positive conclusion is 3.0%, while under the assumption of a maximum reduction versus placebo of 0.5 voids, the power (probability of success) reaches approximately 85 to 90%.

### 3.1.3 Trial Stages

In the first of the two trial stages, an interim Bayesian analysis for futility is performed after 125 subjects have been randomized. The futility stopping rule in the first stage is that a less than 10% posterior probability that 500  $\mu\text{g}$  FE 201836 has  $>0.3$  voids reduction in nocturnal voids as compared to placebo ( $\Pr(\mu_{500} - \mu_{Plb} < -0.3) < 10\%$ ).

The futility stopping rule in the second stage is a less than 5% posterior probability that 500  $\mu\text{g}$  FE 201836 has  $>0.3$  voids reduction in nocturnal voids as compared to placebo ( $\Pr(\mu_{500} - \mu_{Plb} < -0.3) < 5\%$ ).

Bayesian estimates based in the dose-response curve without baseline adjustment will be used to update the allocation probabilities for the different doses of FE 201836 (see Section 12).

### 3.1.4 Trial Epochs

During the screening period, the trial has a 2-week lifestyle-changes period followed by an enrichment phase consisting of a 1-week single-blind active run-in period and a 1-week washout period. The screening period is followed by a 12-week randomized, double-blind treatment period. Thus, the trial has 4 epochs, a lifestyle-changes epoch, a single-blind, active run-in epoch, a washout epoch, and a randomized, double-blind treatment epoch.

### 3.1.5 Visits and Visit Windows

The scheduled measurement time points are presented in [Table 3](#) for primary, secondary, safety, and exploratory endpoints in the order they occur in Section [2.2](#).

**Table 3 Schedule for Assessments of Endpoints According to the Flow Chart in the Protocol.**

Capital X Shows Endpoint-Analyses Time Points, Lowercase x Shows Trial Assessments Not Considered as Endpoints.

Trial Epoch	Life-style Changes	(Start of) Active Run-in	(Start of) Washout	Randomized Trial Period				
				V4 (baseline-RT)	V5	V6	V7	V8
Visit	V1	V2	V3					
Week					1	4	8	12
Planned Day		-14	-7	1	8±2	28±3	56±3	84±7
Endpoints								
Primary Endpoint								
Number of nocturnal voids		x	x	x	X	X	X	X
Secondary Endpoints								
Responder rates derived from number of nocturnal voids					X	X	X	X
NI Diary Total Score		x		x	X	X	X	X
NI Diary Overall Impact Score		x		x	X	X	X	X
PGI-I					X	X	X	X
PGI-S		x		x	X	X	X	X
Bother				x	X	X	X	X
ISI		x		x		X	X	X
FUSP		x	x	x	X	X	X	X
Nocturnal diuresis rate (=NUV / Total sleep)		x	x	x	X			X
NUV		x	x	x	X			X
Safety Endpoints								
Adverse events a			X	X	X	X	X	X
Hyponatremia serum sodium level	x		x	b	X	X	X	X
Total daily urine volume		x		x	X			X
Vital signs	x	X	x	x	X	X	X	X
Laboratory values: Clinical chemistry, haematology, urinalysis	x			x	X	X	X	X
Laboratory values: Coagulation factors	x			x		X		X

Trial Epoch	Life-style Changes	(Start of) Active Run-in	(Start of) Washout	Randomized Trial Period				
				V4 (baseline-RT)	V5	V6	V7	V8
Visit	V1	V2	V3		1	4	8	12
Week								
Planned Day		-14	-7	1	8±2	28±3	56±3	84±7
Endpoints								
Exploratory Endpoints								
NPi (=NUV / Total daily urine volume)		X		x	X			X
Copeptin		X		x				X
Total sleep		x	x	x	X	X	X	X

a AEs are also recorded at a telephone follow-up scheduled at Day -10±1

b Serum Sodium is also measured at Visit 4 as a part of the standard laboratory measurements

For post-randomization Voiding Diary endpoints, the date of completion of the diary (Night 3), will be used for the allocation of the data according to the visit windows. For all other endpoints including pre-randomization Voiding Diary data, the corresponding actual site visit day will be used for the allocation of the data according to the visit windows. The analysis day (ADY) is defined as date of corresponding site visit (Night 3 for post-randomization Voiding Diary data) – date of Visit 4 (day of randomization / baseline of the double-blind treatment period). Visit 4 is defined as Analysis Day 0 and has no visit window for the corresponding site visit date.

For the screening period (the lifestyle-changes epoch, the active run-in epoch, and the washout epoch), the visit windows for all endpoints are linked to the start of the active run-in epoch (the baseline for the enrichment period), that is, the date of the scheduled Visit 2 (VISITNUM=2): All visits before the date of VISITNUM=2 are allocated to the Visit 1 window. All visits after the date of VISITNUM=2 and before the date of VISITNUM=4 are allocated to the Visit 3 window.

Prioritization between multiple visits with non-missing assessment of the endpoint within the same visit window for the screening period will be performed according the following rules, unless otherwise specified:

1. If the assessment is non-missing at the scheduled visit, the assessment at the scheduled visit is used.
2. If the assessment is missing at the scheduled visit, the non-missing assessment closest to the scheduled visit is used.
3. If the assessment is missing at the scheduled visit and the two closest, non-missing assessments from unscheduled visits in the same visit window have equal distances from the date of the scheduled visit, then the latest one will be selected (only relevant for Visit 3).

For the randomized, double-blind treatment epoch, different visit windows will be used for different endpoints. The endpoints fall mainly into two major categories according to when the endpoint is assessed.

Category I comprises efficacy and safety endpoints assessed at all visits during the randomized-treatment period. Efficacy endpoints are Number of Nocturnal Voids and Responder outcomes derived from number of nocturnal voids, NI Diary Total Score, NI Diary Overall Impact Score, PGI-I, PGI-S, Bother, FUSP, and Total Sleep. Safety endpoints are Hyponatremia Serum Sodium Level, Clinical Chemistry, Haematology, Urinalysis, Weight, and Vital Signs.

Category II comprises the efficacy endpoints assessed only at Visits 5 and 8: Nocturnal Diuresis Rate, NUV, and NPi; and the safety endpoint: Total Daily Urine Volume.

The remaining endpoints, the efficacy endpoints ISI and Copeptin and the safety endpoint Coagulation factors, are assessed at different visits. All visit windows for the randomized-treatment period are specified below ([Table 4](#)):

**Table 4 Visit Windows Using Analysis Day Calculated as Site Visit Date – Date of Visit 4.**

Visit Number	Visit windows a			
	5	6	7	8
Visit Week	Week 1	Week 4	Week 8	Week 12
Planned Day According to Protocol	8	28	56	84
Target day b	7	28	56	84
Category I Endpoints	[1, 17]	[18, 42]	[43, 70]	[71, $\infty$ [
Category II Endpoints	[1, 45]	NA	NA	[46, $\infty$ [
ISI	NA	[1, 42]	[43, 70]	[71, $\infty$ [
Copeptin	NA	NA	NA	[1, $\infty$ [
Coagulation factors	NA	[1, 55]	NA	[56, $\infty$ [

a using analysis day derived from the corresponding site visit date

b to be used when prioritizing multiple assessments of an endpoint within the visit window

Prioritization between multiple visits with non-missing assessment of the endpoint within the same visit window will be performed according the following rules, unless otherwise specified:

1. If more than one non-missing assessment of an endpoint fall within the same visit window, the one closest to the target day will be used for that endpoint.
2. If two non-missing assessments in the same visit window have equal distances from the target day, the latest one will be used.

For the first safety interim analysis, the actual visit (VISITNUM) will be used. For the futility interim analyses, the site visit date and the visit windows specified in [Table 4](#) will be used.

#### 4 Major Protocol Deviations

The following protocol deviations are considered major in the sense that they lead to exclusion of subject or subject data from the Per Protocol Set (see Section 5.2.2):

- The subject is excluded in case of <2 nocturnal voids (average over 3 diary nights) prior to Visit 2 or Visit 4
- The subject is excluded in case of NPi  $\leq$  33% prior to Visit 2
- The subject is excluded in case of <20% decrease in nocturnal diuresis rate (mL/min) from during active run-in (Visit 2 to Visit 3)
- The subject is excluded in case of maximum voided volume <200 mL prior to Visit 2
- The subject is excluded in case of actual treatment not in accordance with randomized treatment
- Visit-specific data are excluded in case of significant non-compliant treatment administration for the visit. For each visit, this is defined as e-Diary-registered intake of trial medication for less than half of the nights for which number of nocturnal voids could be derived
- The subject is excluded in case of significant non-compliant e-Diary completion at Visit 4 defined as the Voiding Diary filled out more than 1 week before the site visit for Visit 4
- For Visits 6, 7 and 8, visit-specific data are excluded in case of significant non-compliant e-Diary completion at the visit defined as the Voiding Diary completed more than 2 weeks before or after the planned day according to the protocol (28, 56, and 84 days after Visit 4, respectively). For Visit 5, significant non-compliance is defined as the Voiding Diary completed more than 14 days after Visit 4
- Visit-specific data are excluded in case of current treatment with any of the following prohibited medications:
  - Thiazide diuretics [ATC code: C03AA]
  - V2-receptor antagonists/agonists (e.g., vaptans/desmopressin, vasopressin) [ATC code: C03XA/H01BA]
  - Loperamide [ATC code: A07DA03]
  - Botulinum toxin (cosmetic non-urological use is acceptable) [ATC code: J06AA04]
  - Valproate [ATC code: N03AG01]

Serious unforeseen deviations deemed to impact the primary endpoint of the trial may additionally be rated as major protocol deviations by the sponsor on the basis of a blinded review of data before declaration of clean-file and lock of database. The list of major protocol deviations will be detailed and documented in the clean file document prior to database release to the trial statistician.

## 5 Analysis sets

### 5.1 Enrichment-Period Analysis Sets

#### 5.1.1 Intention-To-Treat Analysis Set for the Enrichment Period (ITT-ENR)

The Intention-to-Treat analysis set for the enrichment period (ITT-ENR) comprises all subjects found to be eligible to enter the enrichment period (comprising 1 week of active run-in and 1 week of washout) at Visit 2. All ITT-ENR analyses will be according to the planned treatment allocation.

#### 5.1.2 Safety Analysis Set for the Enrichment Period (Safety-ENR)

The safety analysis set for the enrichment period (Safety-ENR) comprises all subjects who received investigational medicinal product (IMP) at Visit 2 and did not return all IMP unused at or before Visit 4, based on the drug accountability. This also includes any subject who was found not eligible at Visit 2 but received at least one dose of IMP at or after Visit 2 and before Visit 4 and did not return all IMP unused at or before Visit 4. All safety analyses will be according to actual treatment received.

### 5.2 Randomized-Treatment-Period Analysis Sets

#### 5.2.1 Intention-To-Treat Analysis Set for the Randomized-Treatment Period (ITT-RT)

The Intention-to-Treat analysis set for the randomized-treatment period (ITT-RT) comprises all subjects randomized at Visit 4.

#### 5.2.2 Per Protocol (PP) Analysis Set for the Randomized-Treatment Period

The Per Protocol analysis set comprises all subject data (that is, all combinations of subject and visit) in the ITT-RT analysis set excluding subject data that meet any of the major protocol deviations as defined in Section 4. Subjects for whom all post-baseline data are excluded are not included in the Per Protocol Set.

#### 5.2.3 Safety Analysis Set for the Randomized-Treatment Period (Safety-RT)

The safety analysis set for the randomized-treatment period (Safety-RT) comprises all subjects who received IMP at Visit 4 and did not return all IMP unused, based on the drug accountability, and have had at least one safety assessment after randomization (Visit 4). This also includes any subject who was found not eligible at Visit 4 but who received at least one dose of IMP at or after Visit 4 and did not return all IMP unused. All safety analyses will be according to actual treatment received.

## 6 Trial population

### 6.1 Demographics and Other Baseline Characteristics

#### 6.1.1 General Considerations

The trial has two baselines, one for the enrichment period (denoted baseline-ENR) including the latest data obtained before or at Visit 2, and one for the randomized-treatment period (denoted baseline-RT) including the latest data obtained before or at Visit 4 unless otherwise specified.

#### 6.1.2 Demographics

Baseline-ENR values of the demographics variables: age, sex, race, and ethnic origin, height, weight and BMI will be summarized overall for the ITT-ENR and the Safety-ENR analysis sets. Baseline-RT demographics will be summarized overall and by treatment group for the ITT-RT analysis set.

#### 6.1.3 Vital Signs at Baseline

Baseline-ENR vital signs will be summarized overall for the ITT-ENR analysis set. Baseline-RT vital signs will be summarized overall and by treatment group for the ITT-RT analysis set.

#### 6.1.4 Physical Examination at Baseline

Physical examination at baseline-ENR will be summarized overall for the ITT-ENR analysis set, and physical examination at baseline-RT will be summarized overall and by treatment group for the ITT-RT analysis set.

#### 6.1.5 Laboratory Efficacy Parameters at Baseline

Baseline-ENR copeptin will be summarized for the ITT-ENR analysis set. Baseline-RT copeptin will be summarized overall and by treatment group for the ITT-RT analysis set.

#### 6.1.6 e-Diary Assessments at Baseline

The baseline registrations in the e-Diary include a Voiding Diary, a Nocturia Impact Diary, PGI-S, ISI, and Bother. Based on the baseline registrations in the Voiding Diary, baseline values for several variables are derived: number of nocturnal voids, nocturnal urine volume, NPI, nocturnal diuresis rate, FUSP, and total sleep. The Nocturia Impact Diary is used to derive the baseline values of the two NI Diary endpoints, NI Diary Total Score and the overall QoL impact question.

Baseline-ENR values of the e-Diary variables will be summarized overall for the ITT-ENR analysis set. Baseline-RT values of the e-Diary variables will be summarized overall and by treatment group for the ITT-RT analysis set.

## 6.2 Medical History

Medical history recorded at the screening visit will be coded using the latest version of MedDRA and tabulated by System Organ Class (SOC) and preferred term (PT) and randomized-treatment group (including non-randomized subjects as a separate treatment group) for the Safety-ENR analysis set.

## 7 Subject Disposition

Presentations of subject dispositions will be produced for the overall trial population and by sex.

All subjects screened will be accounted for. All screening failures, protocol violations, and discontinuations from trial will be summarized with frequency and percentage for each category of screening failure reason, protocol violation, and reason for discontinuation, respectively.

All screening failures will be listed in a data listing including the reason(s) for screening failure.

Subject disposition for the ITT-RT analysis set (Section 5.2.1) will be tabulated by treatment group. Reasons for not being randomized at Visit 4 will be categorized and summarized for the ITT-ENR (Section 5.1.1) analysis set. Subject disposition for the safety analysis sets (Sections 5.1.2 and 5.2.3), will be presented separately.

For the ITT-RT analysis set, the treatment-arm (placebo, FE 201836 pooled, desmopressin pooled) differences in time to early discontinuation will be tested using the Log-Rank test, and, for each treatment arm separately, the one-minus-Kaplan-Meier (1-KM) plots of time to early discontinuation will be displayed differentiated by reason for discontinuation. In these analyses, completers will be censored at the maximum of 84 days and the latest observed day of early discontinuation. All early discontinuations will be summarized by time of and reason for discontinuation.

## 8 Prior and Concomitant Medication

Prior and concomitant medication will be summarized by the Anatomical Therapeutic Chemical Classification System (ATC) classification 1st level (alphabetically), ATC classification 2nd level (in decreasing order of frequency) and treatment group. These medications will be tabulated for the Safety-ENR analysis set according to

- 1) Prior medication taken exclusively prior to any treatment with IMP, i.e., with stop date before the date of dispense of first single-blind IMP;
- 2) Concomitant medication taken during the enrichment period, i.e., medication that was not stopped before the date of first single-blind IMP administration and not started after the date of first double-blind IMP administration;
- 3) Concomitant medication taken during the randomized-treatment period, i.e., medication that was not stopped before the date of first double-blind IMP administration and not started after the End-of-Trial Visit.

If the timing of the dose of a concomitant medication cannot be established in relation to the administration of randomized IMP, it will be considered as concomitant medication in both the enrichment period and the randomized-treatment period.

## 9 Exposure and Treatment Compliance

### 9.1.1 Extent of Exposure

#### 9.1.1.1 General Considerations

There are two independent sources for assessment of the extent of exposure: investigator's registration of amount of IMP dispensed and amount of IMP returned, and the subject's e-Diary registrations.

The subjects are always dispensed two sets of IMP, one set of bottles and one set of ODT. Therefore, there are two sets of registrations of IMP accountability at each visit, one for the number of bottles dispensed and returned, and one for the number of ODT dispensed and returned. The investigator registers the amount of IMP dispensed in number of bottles and number of ODT at the scheduled Visits 2, 4, 5, 6, and 7 with dispense of IMP; and the amount of IMP returned in number of bottles and number of ODT at the scheduled Visits 3, 5, 6, 7, and End-of-Trial visit with accountability of IMP.

The subject registers whether he/she took the trial medication in the e-Diary on a daily basis between Visits 2 and 3, and from Visit 4 to End-of-Trial Visit.

The two sources will be summarized separately, and in addition, the agreement between the two sources will be quantified and summarized.

#### 9.1.1.2 Extent of Exposure Based on the Investigator-Assessed Amount of IMP Dispensed and Returned

Extent of exposure is measured both as duration of treatment in number of days and as number of doses. The exposure in number of bottles and the exposure in number of ODT will be summarized separately.

Duration for the active run-in period is derived as the date of the earliest of Visit 3 and End-of-Trial Visit minus the date of Visit 2. Number of doses for the active run-in period is derived as number of doses dispensed at Visit 2 minus number of doses returned at the earliest of Visit 3 and End-of-Trial Visit. Duration and number of doses during the active run-in period will be summarized overall and by sex for the ITT-ENR analysis set and for the Safety-ENR analysis set.

For each of the post-randomization visits with registration of amount of IMP returned, the duration in the preceding period between visits will be derived as the difference between the date of the current visit and the date of the previous visit with IMP accountability. The number of doses will be calculated as the number of doses dispensed at the previous visit with IMP accountability minus the number of doses returned at the current visit. If two or more visits with IMP accountability fall into the same visit window, the duration will be summed across the visits and the number of doses will be summed across the visits.

The duration and the number of doses will be summarized by treatment group and visit, overall and by sex, for the ITT-RT analysis set and for the Safety-RT analysis set.

Duration for the whole randomized-treatment period is derived as the date of the End-of-Trial Visit minus the date of Visit 4 and will be summarized by treatment group for the ITT-RT analysis set and for the Safety-RT analysis set. Number of doses for the whole randomized-treatment period is derived as the sum of the doses across the post-randomization visits and will be summarized by treatment group for the ITT-RT analysis set and for the Safety-RT analysis set.

Total duration will be derived as the difference between the date of the End-of-Trial Visit and the date of Visit 2. Total extent of exposure in number of doses will be derived as the sum of the doses in the enrichment period and the doses in the randomized-treatment period. Total duration and total extent of exposure in number of doses will be summarized by treatment group for the ITT-RT analysis set and for the Safety-RT analysis set.

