5.6.2 Assessment of Compliance

Treatment compliance will be verified at Visits 3, 5, 6, 7 and 8, by reviewing the used, partly used and unused IMP and/or subject's statements documented in the source documents in case the IMP is lost.

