### 9.1.2 Treatment Compliance

Compliance will be derived separately for each of the three exposure measures of number of doses: the number of bottles and the number of ODT (Section 9.1.1.2), and the number of doses according to the e-Diary (Section 9.1.1.3). For each exposure measure of number of doses, compliance in % during a specific period (that is, a period between two visits, the active run-in period, the randomized-treatment period, or total exposure duration) will be derived as the exposure measure of number of doses for the period divided by the corresponding exposure duration in days for the same period calculated in Section 9.1.1.2 as the end date minus the start date of the period, and multiplied by 100 to obtain a percentage.

Compliance during the active run-in period will be summarized as overall and by sex for the ITT-ENR analysis set and for the Safety-ENR analysis set.

Compliance will be summarized by treatment group and visit, overall and by sex, for the ITT-RT analysis set and for the Safety-RT analysis set.

In addition, for each visit with Voiding Diary assessments, treatment compliance will be derived for the nights where the number of nocturnal voids can be derived. The treatment compliance in % during Voiding Diary assessment will be derived as the number of nights where the number of nocturnal voids can be derived and the subject answered Yes to “*Did you take your study medication during this diary day?*” divided by the total number of nights where the number of nocturnal voids can be derived in the Voiding Diary for the visit, and multiplied by 100 to obtain a percentage. Treatment compliance during Voiding Diary assessment will be summarized as a categorical variable by treatment group and visit for the ITT-RT analysis set and for the PP analysis data set.

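### SAP 9.1.1.2 counts the drug-free washout in total exposure duration, so total duration is about 7 days too long and total compliance cannot reach 100%

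*SAP*

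**What the plan says.** SAP 9.1.1.2 measures extent of exposure in two ways, as days of treatment and as doses. It gives three durations:

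- Run-in: Visit 3 (or End-of-Trial, if earlier) minus Visit 2.
- Randomised period: End-of-Trial minus Visit 4.
- Total: "Total duration will be derived as the difference between the date of the End-of-Trial Visit and the date of Visit 2".

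The total number of doses is additive over the run-in and the randomised period. The rule begins "Total extent of exposure in number of doses will be derived as the sum of the doses in the enrichment period and the doses in" and goes on to name the randomised period. Total duration and total doses are both summarised by treatment group for ITT-RT and Safety-RT.

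SAP 9.1.2 defines compliance as a dose count "divided by the corresponding exposure duration in days for the same period calculated in Section 9.1.1.2". It names the periods to which this applies: "a period between two visits, the active run-in period, the randomized-treatment period, or total exposure duration". The rule covers all three dose measures (bottles, ODT and e-Diary).

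No drug is given in the washout. Protocol Table 5-1 shows dashes for it, and SAP 9.1.1.1 has subjects record intake only from Visit 2 to Visit 3 and from Visit 4 onwards.

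For the separate visit-by-visit figures, SAP 9.1.1.2 takes the duration as "the difference between the date of the current visit and the date of the previous visit with IMP accountability", and the doses as those dispensed at that earlier visit minus those returned at the current one. SAP 9.1.1.1 lists dispensing at Visits 2, 4, 5, 6 and 7. It lists returns at Visits 3, 5, 6 and 7 "and End-of-Trial visit with accountability of IMP". Protocol 5.6.2 matches the list of return visits: "Treatment compliance will be verified at Visits 3, 5, 6, 7 and 8".

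**The concern.** The numerator of total compliance covers two dosing periods. The denominator covers those two periods plus the gap between them, during which the protocol gives nothing to take. A subject who is fully compliant in each period is then reported as less than fully compliant over both together.

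The shortfall is not a constant that a reader could subtract. The washout is a fixed block of days, so it weighs more the sooner a subject leaves the trial. The protocol's simulations assume 15% dropout. If dropout differed between arms, total compliance would differ too, even with perfect adherence in every arm. Total duration would also be reported as longer treatment than anyone received.

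**Working it through.** The plan states no compliance figure to reproduce, so the check applies its rules to a perfectly adherent subject.

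**Inputs**

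- Run-in 7 days and washout 7 days (SAP 3.1.4).
- Visit 5 at 7 days and Visit 8 at 84 days after Visit 4 (target days in SAP Table 4).
- One dose per night (Protocol 5.1).
- Setting Visit 4 = day 0: Visit 2 = −14, Visit 3 = −7, Visit 5 = 7, End-of-Trial = 84.

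**Component periods**

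- Run-in: −7 − (−14) = 7 days, 7 doses, 7/7 = 100%.
- Randomised: 84 − 0 = 84 days, 84 doses, 84/84 = 100%.

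**Total as written**

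- Doses: 7 + 84 = 91.
- Duration: 84 − (−14) = 98 days, against 7 + 84 = 91 days of treatment. The excess is 7 days, or 7/91 = 7.7%.
- Compliance: 91/98 = 92.9%.

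**Total for early leavers**, still perfectly adherent up to the End-of-Trial Visit

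| End-of-Trial at | Doses | Duration as written | Compliance as written | Duration without washout | Compliance without washout |
|---|---|---|---|---|---|
| Week 12 | 7 + 84 = 91 | 98 | 92.9% | 91 | 100% |
| Week 4 | 7 + 28 = 35 | 42 | 83.3% | 35 | 100% |
| Week 1 | 7 + 7 = 14 | 21 | 66.7% | 14 | 100% |

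**Sensitivity for a completer**

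- Visit 8 seven days early: 84/91 = 92.3%. Seven days late: 98/105 = 93.3%.
- Subtracting the flow-chart day labels directly (Visit 4 = 1, Visit 8 = 84) makes the washout 8 days and the randomised period 83: 90/98 = 91.8%.
- A 10-day washout: 91/101 = 90.1%.

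**Visit 5 period, secondary point**

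If accountability means only the visits listed with returns, the Visit 5 period starts at Visit 3.

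- Duration: 7 − (−7) = 14 days. The e-Diary count gives 7/14 = 50% (5/12 = 41.7% to 9/16 = 56.2% over the ±2-day Visit 5 window).
- Bottles and ODT: dispensed at Visit 3 (none) minus returned at Visit 5, which is zero or negative.

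If the period starts at Visit 4, it is 7/7 = 100%. Only this start fits the rest of the section. With Visits 6 and 7 at days 28 and 56, the four between-visit durations add to 7 + 21 + 28 + 28 = 84, which is the SAP's own randomised-period duration. Starting at Visit 3 they add to 14 + 21 + 28 + 28 = 91.

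**The case against.** The best case for leaving the text alone has four parts.

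- **Correct figures are already planned.** The run-in and randomised-period durations exclude the washout, so compliance for each period is right. This stands, and it limits the problem to the totals.
- **No total-compliance table is expressly specified.** SAP 9.1.2 makes total compliance derivable, but the summaries it names are for the run-in and by treatment group and visit. Protocol 9.9 likewise asks for treatment group and visit period. This stands in part: total duration is expressly summarised, and the total ratio is defined, so it will be wrong wherever it is produced.
- **The washout precedes randomisation.** Its length cannot depend on the assigned arm, so completers gain about 7 days in every arm. This is true for duration. It does not protect the ratio, because the same 7 days cost an early leaver far more than a completer.
- **Nothing inferential depends on it.** The per-protocol rule in SAP Section 4 uses recorded intake on nights for which nocturnal voids can be derived, not this ratio. This stands.

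A reader might infer more from the Visit 5 wording: that Week 1 compliance will be reported as 50%, or that the 7 Week 1 doses drop out of the randomised total of 84. The documents do not support that as the plan. SAP 9.1.1.1 also speaks of accountability for drug both dispensed and returned at each visit, which can include Visit 4. The dose rule presupposes dispensing at the earlier visit, and nothing is dispensed at Visit 3. The 50% holds only for the e-Diary count under the literal reading. Losing 7 bottle or ODT doses is also incompatible with 92.9%, which counts all 84 randomised doses; with the loss, the total would be 84/98 = 85.7% or lower. What remains is an ambiguous term.

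**Conclusion.** The total-duration rule is wrong as written, and no other reading of it is available. Total duration is overstated by the length of the washout, about 7 days, and total compliance for perfect adherence is 92.9% for a completer (91.8% to 93.3% over the Visit 8 window and day-numbering conventions), 83.3% at Week 4 and 66.7% at Week 1. These figures assume the nominal one-week run-in and washout, one dose per night, and dosing up to the End-of-Trial Visit.

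The effect is confined to descriptive total-exposure and total-compliance figures. It would be wrong to conclude that every compliance table is understated, or that the per-protocol set, the primary analysis or proof-of-concept is affected. The start of the Visit 5 period is a separate, lesser matter of unclear wording, where the surrounding text points to Visit 4.

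**What to change.** **Main change, one sentence in SAP 9.1.1.2.** Define total duration as (Visit 3 − Visit 2) + (End-of-Trial − Visit 4), and state in 9.1.2 that this is the denominator for total compliance. Perfect adherence then gives 91/91 = 100% for a completer, and 100% at any withdrawal time in the table above.

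**Secondary clarification, one phrase in SAP 9.1.1.2.** Start each post-randomisation between-visit period at the preceding visit at which drug was dispensed, for both duration and doses. For Visit 5 this is Visit 4.

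All the dates and counts needed are already collected. Neither change touches treatment, visits or any inferential analysis, and the cost is the SAP edit and the matching line in the programming specification.
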